7.2.4 AE Outcomes

The following terms and definitions are used in assessing the final outcome of an AE:

- Recovered/Resolved The patient has fully recovered, or by medical or surgical treatment, the condition has returned to the level observed at the first trial-related activity.
- Recovering/Resolving The condition is improving and the patient is expected to recover from the event.
- Recovered/Resolved with sequelae The patient has recovered from the condition, but with lasting effect due to a disease, injury, treatment or procedure. If a sequela meets an SAE criterion, the AE must be reported as an SAE.
- Not recovered/Not resolved The condition of the patient has not improved and the symptoms are unchanged, or the outcome is not known at the time of reporting.
- Fatal This term is only applicable if the patient died from a condition related to the reported AE. Outcomes of other reported AEs in a patient before he/she died should be assessed as "recovered", "recovering", "recovered with sequelae" or "not recovered". An AE with fatal outcome must be reported as an SAE.

7.2.5 Laboratory Test and other Test Abnormalities as Adverse Events

A laboratory or other test (chest assessments, vital signs) abnormality should be reported as an AE if the Investigator considers the abnormality an AE or if the abnormality is associated with accompanying symptoms, requires medical/surgical intervention, leads to a change in study treatment, or results in discontinuation from the trial. When possible, syndromes not laboratory values, should be reported as AEs. For example, elevated hepatic transaminases associated with hepatitis should be reported as "hepatitis" and decreased hemoglobin and hematocrit requiring iron supplementation should be recorded as "anemia." Prior to reporting as an AE, abnormal tests should be repeated to verify the accuracy of the original result.

7.2.6 Serious Adverse Events

The Investigator is required to determine if each AE is a Serious Adverse Event (SAE). An SAE is any AE occurring after the first dose of study medication and results in any of the following outcomes:

- Death, or
- Is life-threatening, or
- Prolongation of existing hospitalization, or
- Results in a persistent or significant incapacity or substantial disruption of the ability to conduct normal life functions, or
- Is a congenital anomaly/birth defect.

Important medical events that may not result in death, be life threatening, or require hospitalization may be considered SAEs when, based upon appropriate medical

judgment, they may jeopardize the patient and may require medical or surgical intervention to prevent one of the outcomes listed in this definition.

In the event of death, the cause of death should be recorded as the SAE (death is an outcome, not the AE itself).

Any planned procedures that require admission to hospital as well as any planned elective procedures (e.g., angioplasty) are not considered SAEs (unless the underlying condition has worsened or the procedure results in a worsening of the patient's condition). In addition, pregnancy that occurs during the course of the study or absence of a treatment effect will also not be considered to be an SAE and will be collected on a separate CRF.

7.2.7 Reporting for SAEs (24 Hours)

Regardless of causality, an SAE must be followed clinically until resolution or stabilization.

All SAEs after the first dose of study medication through Day 28 of the study must be reported to the Sponsor or the Sponsor's representative within 24 hours of the investigational site's knowledge of the occurrence. The investigational site will email a Serious Adverse Event Report (SAER) to the Sponsor and the Medical Monitor. Investigational sites will be provided with SAER forms. The Medical Monitor will work closely with the Sponsor to properly assess and report the SAE.

The SAE information emailed to the Sponsor or the Sponsor's representative will include the following (as available):

- Patient Number, Investigator name, and Site Number
- SAE information: event term, onset date, severity, and causal relationship
- Basic demographic information (e.g., age, gender, weight)
- The outcomes attributable to the event (death, a life-threatening adverse drug experience, inpatient hospitalization or prolongation of existing hospitalization, a persistent or significant disability/incapacity, other important medical event[s])
- A summary of relevant test results, pertinent laboratory data, and any other relevant medical history
- The first and last dates of study medication administration
- A statement whether study medication was discontinued or study medication administration schedule modified
- A statement whether event recurred after reintroduction of study medication if administration had been discontinued or withheld
- Supplemental anonymized information may include the following hospital records: laboratory results, radiology reports, progress notes, admission and emergency room notes, holding/observation notes, discharge summaries, autopsy reports, and death certificates

Supplemental information may be transmitted using a follow-up report and should not delay the initial report.

For regulatory purposes, initial reports of SAEs should be transmitted within the prescribed time frame as long as the following minimum information is available: patient number, suspect study medication, reporting source, and an event or outcome that can be identified as being both serious and unexpected for which the Investigator can make a relationship assessment.

7.3 Reporting of Pregnancy

Any pregnancy where the estimated date of conception occurs either prior to the End of Study must be reported.

If an adverse outcome of a pregnancy is suspected to be related to study medication exposure, this should be reported regardless of the length of time that has passed since the exposure to study treatment.

An induced abortion or a spontaneous abortion is considered to be an SAE and should be reported in the same timeframe and in the same format as all other SAEs.

Pregnancies must be reported as soon as possible but no later than one business day by email.

All pregnancies must be followed to outcome. The outcome of the pregnancy must be reported as soon as possible but not later than 24 hours of the investigational site's knowledge of the outcome.

8. PHARMACOKINETIC ASSESSMENTS

Not applicable.

9. SCHEDULE OF ASSESSMENTS AND PROCEDURES

The assessments and procedures for this study are described in detail below and presented in the Schedule of Assessments and Procedures located behind the Synopsis.

9.1 Study Evaluation Timepoints

9.1.1 Screening (within 14 days prior to Baseline Day 1)

Potential study patients will be recruited by the study staff from patients. The following assessments will occur prior to study enrollment:

- Informed consent prior to any study procedures or assessments being performed.
- Demographic Information
- Medical History
- Physical Exam

- Prior Medication History
- Chest CT or Chest X-ray
- Inclusion/Exclusion Eligibility Assessment (including assessment of shortness of breath within the last 14 days)
- Serum/Urine Pregnancy Test (if woman of childbearing potential)
- Clinical Laboratory Sampling to include: Full Chemistry Panel including LFTs, CBC with Diff including neutrophils and lymphocytes, PT/PTT, Triglycerides, LDH, ferritin, fibrinogen, CRP, ESR, IL-6, troponin, BNP, D-Dimer, and RT-PCR for COVID-19
- Vital Signs
- Height & Weight (If height can't be obtained, use the best reported historical height)

9.1.2 Days 1-10 Treatment

9.1.2.1 Baseline-Day 1 (0 Hour)

- Continue evaluation eligibility by assessing Inclusion/Exclusion Criteria.
- Subjects will receive VentaProst, for a maximum of 10 days, as clinically indicated at the discretion of the Investigator. VentaProst dose will begin at 13.6 ng/kg/min and can be titrated up to 30.6 ng/kg/min or down to 3.4 ng/kg/min as clinically warranted. The B.Braun syringe pump will be set to the appropriate dose utilizing the subject's sex and height (ideal body weight).
- Vital signs will be assessed twice daily in AM and PM while on VentaProst. Efforts will be made to obtain vital signs at the same time each day. Vital signs include: temperature, pulse rate, respiration rate and blood pressure.
- Adverse Event/SAE assessment daily
- Concomitant medication evaluation daily
- Continuous pulse oximetry (SpO₂)
- Ventilatory parameters assessed twice daily while on VentaProst: Ventilator Type, Vent Mode, FiO₂, Inspiratory time, Mean Airway Pressure, Peak Inspiratory Pressure, Positive End Expiratory Pressure, Tidal Volume, and Respiratory Rate
- Time Prone Position-16 hours per day per OSU Protocol

9.1.2.2 Day 1-12 hours

- Clinical Laboratory Sampling to include: Full Chemistry Panel including LFTs, CBC with Diff including neutrophils and lymphocytes, PT/PTT, Triglycerides, LDH, ferritin, fibrinogen, CRP, ESR, IL-6, troponin, BNP, and D-Dimer.
- Continue to administer VentaProst if clinically indicated.

- Adverse Event/SAE assessment daily
- Concomitant medication evaluation daily
- Oxygenation measurement via continuous pulse oximetry (SpO₂)
- Ventilatory parameters assessed twice daily while on VP: Ventilator Type, Vent Mode, FiO₂, Inspiratory time, Mean Airway Pressure, Peak Inspiratory Pressure, Positive End Expiratory Pressure, Tidal Volume, and Respiratory Rate
- Vital signs will be assessed twice daily in AM and PM. Efforts will be made to obtain vital signs at the same time each day. Vital signs include: temperature, pulse rate, and blood pressure.
- Time Prone Position-16 hours per day per OSU Protocol

9.1.2.3 Days 2-10 (While on VentaProst)

- Continue to administer VentaProst if clinically indicated.
- Adverse Event/SAE assessment daily
- Concomitant medication evaluation daily
- Oxygenation measurement via continuous pulse oximetry (SpO₂)
- Ventilatory parameters assessed twice daily: Ventilator Type, Vent Mode, FiO₂, Inspiratory time, Mean Airway Pressure, Peak Inspiratory Pressure, Positive End Expiratory Pressure, Tidal Volume, and Respiratory Rate
- Vital signs will be assessed twice daily in AM and PM. Efforts will be made to obtain vital signs at the same time each day. Vital signs include: temperature, pulse rate, and blood pressure.
- Time Prone Position-16 hours per day per OSU Protocol
- Full Chemistry Panel including LFTs, CBC with Diff including neutrophils and lymphocytes, PT/PTT and RT-PCR for COVID-19. (Day 5 only)
- Chest CT or Chest X-ray (Day 5 only)
- Full Chemistry Panel including LFTs, CBC with Diff including neutrophils and lymphocytes, PT/PTT, Triglycerides, LDH, ferritin, fibrinogen, CRP, ESR, IL-6, troponin, BNP, D-Dimer, and RT-PCR for COVID-19 (Day 10 only).
- Obtain weight. (Day 10 only or at end of VP dosing)

9.1.2.4 Weaning

Patients will be weaned from VentaProst slowly due to concern that VentaProst is providing significant clinical benefit and to avoid a rebound effect. Doses will be

decreased in steps of 3.4 ng/kg/min increments with a minimum of 15 minutes between changes until VentaProst is discontinued.

9.1.3 Day 28/End of Study (EOS)

- Assess AEs/SAEs
- Assess Mortality
- Assess concomitant medications

9.2 Data Collection

Investigator or designee will enter the information required by the protocol onto source documents and enter data into data collection forms (DCFs) in an excel spreadsheet provided by Aerogen Pharma.

9.3 Clinical Data Management

Data from source documents will be verified against the DCF and any discrepancies will be clarified and resolved with study staff.

9.4 Database Quality Assurance

All databases will be remotely monitored by the Sponsor due to the COVID-19 pandemic. Should restrictions be lifted at OSU, an on-site visit may occur if all parties are in agreement.

10. STATISTICAL CONSIDERATIONS

10.1 Statistical Methods

A Statistical Analysis Plan will be not be developed as this is an exploratory trial. Any statistical evaluation will be handled internally by Aerogen Pharma or their designee.

10.2 Determination of Sample Size

The number of patients has been selected to enable an adequate clinical assessment of pharmacodynamics, safety, and tolerability parameters without presenting undue risk to a large number of patient's being exposed to this investigational product.

10.3 Analyses Sets

All patients who are enrolled in the study and who receive at least one dose of VentaProst will be included in the intent-to-treat (ITT) analyses of pharmacodynamic and safety data. All available data will be used and missing data will not be estimated or carried forward in any statistical summary or analyses.

Descriptive summary statistics include the number of patients, mean, median, percent coefficient of variation (% CV) (if required), standard deviation, and minimum and maximum values (quantitative variables) or the number of patients and percentages by category (qualitative variables). Changes will be assessed as the difference between baseline measurements and the appropriate post-dose measurements unless otherwise

specified. Mean differences between active and historical control groups (when available) will be assessed and significance will be determined on the basis of a 95% CI. Individual patient listings of data will also be provided to allow for review of all pharmacodynamic, safety, and tolerability parameters.

10.4 Demographic and Other Baseline Characteristics

Continuous demographic and other baseline characteristics (such as age, weight, and height) will be summarized using n, mean, SD, median, minimum, and maximum. Qualitative characteristics (such as gender and race) will be summarized by counts and percentages.

10.5 Criteria for Evaluation

10.5.1 Primary Efficacy Endpoint

The primary efficacy endpoint:

- 1. Reduction of respiratory failure. Failure is defined by any one of the following:
 - Requires VV ECMO
 - Inability to extubate patient within 10 days or reintubation within <24 hours
 - Change in S/F, oxygenation index and P/F ratio (≥15%) from baseline to 12 hours, Days 1, 2, 3, 4, 5, 6, 7, 8, 9 and Day 10 (or end of treatment)

or

- 2. Reduction of cardiac or circulatory failure. Failure is defined by any one of the following:
 - Need to begin inotropic or 10% increase in current vasopressor therapy
 - Worsening hemodynamic parameters
 - Cardiac troponin >20 % from baseline
 - BNP > 15% of baseline
 - Need for temporary mechanical circulatory support (IABP, Impella)
 - Requires VA ECMO

10.5.2 Secondary Efficacy Endpoints

Key secondary endpoints include:

- 1. Improvement in oxygenation defined as any one of the following:
 - Stabilization of PaO2/FIO2 >250
 - Improvement in FIO2 by 50% or improvements ≥15% in S/F, P/F ratio from baseline at 12 hours, Day 5 and Day 10 (or end of treatment)
- 2. Improved clinical outcomes defined as one of more of the following:

- Time to extubation following the site's extubation protocol
- Free from reintubation
- Reduction in ICU days
- Reduction in the number of re-admissions to the ICU due to COVID-19 within 28 days
- Reduction in total hospital days
- Mortality [28 days] defined as Cardiopulmonary mortality from all causes

3. Safety

 Monitoring of adverse events (AEs), serious adverse events (SAEs), chest CT or Chest X-rays, vital signs, ventilatory/oxygenation parameters, and laboratory tests.

10.5.3 Key Exploratory Endpoints include:

- Change in LDH
- Change in fibrinogen
- Change in WBC count including lymphocytes and neutrophil subsets
- Change in triglycerides
- Change in ferritin
- Change in CRP / ESR
- Change in IL-6
- Change in D-Dimer

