Chest CT Scan or CXR	X						X						
Clinical Laboratory Sampling ²	X		X				X					X	
Pregnancy Test (Serum or Urine)	X												
RT-PCR + for COVID-19	X						X					X	
Administer VentaProst		X	X	X	X	X	X	X	X	X	X	X	
Vital Signs ³	X	X	X	X	X	X	X	X	X	X	X	X	
Oxygenation Measurements ⁴		X	X	X	X	X	X	X	X	X	X	X	
Ventilator Parameters ⁵		X	X	X	X	X	X	X	X	X	X	X	
AE/SAE Monitoring		X	X	X	X	X	X	X	X	X	X	X	X
Concomitant Medications		X	X	X	X	X	X	X	X	X	X	X	X
Prone position 1 Height only performed a	at screening	X	X	X	X	X	X	X	X	X	X	X	

¹ Height only performed at screening

² Clinical Labs include: Safety labs: CBC (lymphocyte and neutrophil counts), Full Chemistry Panel (including LFTs) and PT/PTT drawn Screening, Day 1-12 hours, Days 5 & 10. Triglycerides, LDH, ferritin, fibrinogen, CRP, ESR, IL-6, D-Dimer, troponin, BNP drawn at Screening, Day 1-12 hours and D-10.

³ Vital signs: Prior to initiating VentaProst, Days 1-10 twice daily (morning and evening) at the same time to reduce exposure to Health Care Professionals to include; temperature, pulse rate, blood pressure.

⁴Continuous SpO2 via pulse oximetry

⁵ Ventilator Parameters will be collected twice daily along with vital signs and include: Ventilator Type, Ventilator Mode, FiO₂, Inspiratory Time, Mean Airway Pressure, Peak Inspiratory Pressure, Positive End Expiratory Pressure, Tidal Volume and Respiratory Rate

⁶Time Prone Position – 16 hours per day per OSU protocol

TABLE OF CONTENTS

INV	/ESTI	GATOR'S SIGNATURE PAGE	3
1.	CLI	NICAL PROTOCOL SYNOPSIS	4
TA	BLE (OF CONTENTS	10
		ACRONYMS, ABBREVIATIONS AND	
		TION OF TERMS	13
2.	BAC	CKGROUND AND RATIONALE	16
	2.1	Introduction	
	2.2	VentaProst	
		2.2.1 Nonclinical Experience	17

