Clinical Laboratory Sampling ²	X		X				X					X	
Pregnancy Test (Serum or Urine)	X												
RT-PCR + for COVID-19	X						X					X	
Administer VentaProst		X	X	X	X	X	X	X	X	X	X	X	
Vital Signs ³	X	X	X	X	X	X	X	X	X	X	X	X	
Oxygenation Measurements ⁴		X	X	X	X	X	X	X	X	X	X	X	
Ventilator Parameters ⁵		X	X	X	X	X	X	X	X	X	X	X	
AE/SAE Monitoring		X	X	X	X	X	X	X	X	X	X	X	X
Concomitant Medications		X	X	X	X	X	X	X	X	X	X	X	X
Prone position 1 Height only performed		X	X	X	X	X	X	X	X	X	X	X	

¹ Height only performed at screening

² Clinical Labs include: Safety labs: CBC (lymphocyte and neutrophil counts), Full Chemistry Panel (including LFTs) and PT/PTT drawn Screening, Day 1-12 hours, Days 5 & 10. Triglycerides, LDH, ferritin, fibrinogen, CRP, ESR, IL-6, D-Dimer, troponin, BNP drawn at Screening, Day 1-12 hours and D-10.

³ Vital signs: Prior to initiating VentaProst, Days 1-10 twice daily (morning and evening) at the same time to reduce exposure to Health Care Professionals to include; temperature, pulse rate, blood pressure.

⁴ Continuous SpO2 via pulse oximetry

⁵ Ventilator Parameters will be collected twice daily along with vital signs and include: Ventilator Type, Ventilator Mode, FiO₂, Inspiratory Time, Mean Airway Pressure, Peak Inspiratory Pressure, Positive End Expiratory Pressure, Tidal Volume and Respiratory Rate

⁶Time Prone Position – 16 hours per day per OSU protocol

TABLE OF CONTENTS

INV	VESTI	GATOR'S SIGNATURE PAGE	9
1.	CLI	NICAL PROTOCOL SYNOPSIS	4
TA		OF CONTENTS	
		ACRONYMS, ABBREVIATIONS AND	
		PION OF TERMS	13
2.		CKGROUND AND RATIONALE	
	2.1	Introduction	
	2.2	VentaProst	

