Chemistry (including AST, ALT, AP, T. Bili) CBC, PT/PTT	X						X					X	
Pregnancy Test (Serum or Urine)	X												
COVID-19 diagnostic test such as molecular or antigen test	X												
Cardiac Troponin, and BNP	X						X					X	
Other blood tests: fibrinogen, ferritin, LDH, Triglycerides, D-Dimer, IL-6, ESR,CRP ⁴	X						X					X	
Administer VentaProst		X	X	X	X	X	X	X	X	X	X	X	
Vital Signs ⁵	X	X	X	X	X	X	X	X	X	X	X	X	
Oxygenation Measurements ⁶		X	X	X	X	X	X	X	X	X	X	X	
Ventilator Parameters ⁷		X	X	X	X	X	X	X	X	X	X	X	
AE/SAE Monitoring		X	X	X	X	X	X	X	X	X	X	X	X
Concomitant Medications		X	X	X	X	X	X	X	X	X	X	X	X
Prone position ⁸		X	X	X	X	X	X	X	X	X	X	X	

- ¹ Informed consent may be obtained after screening study procedures that were conducted as a part of the patient's standard of care.
- ² Height only performed at screening
- ³ Chest CT or CXR may be performed anywhere from 3-8 days as clinically warranted.
- ⁴ These tests are collected only if available as Standard of Care
- ⁵ Vital signs: Prior to initiating VentaProst, Days 1-10 twice daily (morning and evening) at the same time to reduce exposure to Health Care Professionals to include; temperature, pulse rate, blood pressure.
- ⁶Continuous SpO2 via pulse oximetry
- Ventilator Parameters will be collected twice daily along with vital signs and include: Ventilator Type, Ventilator Mode, FiO₂, Inspiratory Time, Mean Airway Pressure, Peak Inspiratory Pressure, Positive End Expiratory Pressure, Tidal Volume and Respiratory Rate
- ⁸Time Prone Position 16 hours per day per OSU protocol

TABLE OF CONTENTS

INV	ESTIG.	ATOR'S SIGNATURE PAGE	3
1.	CLIN	IICAL PROTOCOL SYNOPSIS	4
TAE	BLE O	F CONTENTS	11
		ACRONYMS, ABBREVIATIONS AND	
		ION OF TERMS	14
2.	BACI	KGROUND AND RATIONALE	17
	2.1	Introduction	
	2.2	VentaProst	

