5.4.2 Ventilator Settings

The device is designed for use with standard adult ventilator settings. An intermittent positive pressure ventilatory mode (i.e., not constant positive airway pressure [CPAP] or t-piece) is required to activate the device to deliver aerosol during the inspiration phase. A Heat-Moisture Exchanger (HME) may be used in the device circuit.

The site will utilize OSU's Standard of Care (SOC) mechanical ventilation guidelines for care of patients for COVID-19 with ARDS. The following ventilator parameters will be assessed daily while on VentaProst: Ventilator type, Mode, FiO₂, Inspiratory Time, Mean Airway Pressure, Peak Inspiratory Pressure, Positive End Expiratory Pressure, Respiratory Rate and Tidal Volume.

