6. CRITERIA FOR EVALUATION

6.1 Primary Endpoint

- 1. Reduction of respiratory failure. Failure is defined by any one of the following:
 - Requires VV ECMO
 - Inability to extubate within 10 days or reintubation within < 24 hours
 - Change in S/F, oxygenation index and P/F ratio (≥15%) from baseline to 12 hours, Days 1, 2, 3, 4, 5, 6, 7, 8, 9 and Day 10 (or end of treatment)

or

- 2. Reduction of cardiac or circulatory failure. Failure is defined by any one of the following:
 - Need to begin inotropic therapy or 10% increase in current vasopressor therapy
 - Worsening hemodynamic parameters
 - Cardiac troponin >20% from baseline
 - BNP > 15% of baseline
 - Need for temporary mechanical circulatory support (IABP, Impella)
 - Requires VA ECMO

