9.1.2.4 Days 2-10 (While on study drug)

- Continue to administer study drug if clinically indicated.
- Adverse Event/SAE assessment daily
- Concomitant medication evaluation daily
- Oxygenation measurement via continuous pulse oximetry (SpO₂)
- Ventilatory parameters assessed twice daily: Ventilator Type, Vent Mode, FiO₂, Inspiratory time, Mean Airway Pressure, Peak Inspiratory Pressure, Positive End Expiratory Pressure, Tidal Volume, and Respiratory Rate
- Vital signs will be assessed twice daily in AM and PM. Efforts will be made to obtain vital signs at the same time each day. Vital signs include: temperature, pulse rate, and blood pressure.
- Time Prone Position-16 hours per day per OSU Protocol

- Chest X-ray (Days 3-8 as clinically indicated)
- Full Chemistry Panel including LFTs, CBC with Diff including neutrophils and lymphocytes, PT/PTT, troponin, and BNP(Days 5 & 10).
- Triglycerides, LDH, ferritin, fibrinogen, CRP, ESR, IL 6 and D-Dimer may be collected if the subject's condition warrants it at Days 5 and Day 10.
- Obtain weight. (Day 10 only or at end of study drug dosing)

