10.6.2 Secondary Efficacy Endpoints

Key secondary endpoints include:

- 1. Improvement in oxygenation defined as any one of the following:
 - Stabilization of PaO2/FIO2 >250
 - Improvement in FIO2 by 50% or improvements ≥15% in S/F, P/F ratio from baseline at 12 hours, Day 5 and Day 10 (or end of treatment)
- 2. Improved clinical outcomes defined as one of more of the following:
 - Time to extubation following the site's extubation protocol
 - Free from reintubation
 - Reduction in ICU days
 - Reduction in the number of re-admissions to the ICU due to COVID-19 within 28 days
 - Reduction in total hospital days
 - Mortality [28 days] defined as Cardiopulmonary mortality from all causes
- 3. Safety
 - Monitoring of adverse events (AEs), serious adverse events (SAEs), chest CT or Chest X-rays, vital signs, ventilatory/oxygenation parameters, and laboratory tests.

10.6.3 Key Exploratory Endpoints include:

- Change in LDH
- Change in fibrinogen
- Change in WBC count including lymphocytes and neutrophil subsets
- Change in triglycerides
- Change in ferritin
- Change in CRP / ESR
- Change in IL-6
- Change in D-Dimer

Changes in these parameters will be assessed for each patient from baseline to end of study as well as changes between the active and control groups.

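### The S/F part of the oxygenation secondary endpoint is a responder rule read at three times, and no continuous, baseline-adjusted comparison of the twice-daily S/F data is planned

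*Combined protocol and SAP*

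**What the plan says.** The S/F, P/F and FiO2 criterion is "Improvement in FIO2 by 50% or improvements ≥15% in S/F, P/F ratio from baseline at 12 hours, Day 5 and Day 10"; the end of treatment may stand in for the last of these times. The wording is the same in 10.5.2 of the superseded open-label version and in 6.2 and 10.6.2 of the current double-blind version, which randomizes about 20 patients 1:1. The endpoint is also met through a second criterion, "Stabilization of PaO2/FIO2 >250", which has no time point. Either criterion is enough.

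On data collection, the Table 2 footnotes of the current version say "Ventilator Parameters will be collected twice daily along with vital signs" (FiO2 is in that list) and "Continuous SpO2 via pulse oximetry". Section 9.1.2.4 agrees: "Ventilatory parameters assessed twice daily". Section 5.4.2 differs: "The following ventilator parameters will be assessed daily while on VentaProst".

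On analysis, Section 10.1 says that no SAP will be written. Section 10.3 gives general rules: changes are differences from baseline, mean differences between arms are judged by a 95% CI, all available data are used and nothing is imputed. The synopsis adds a summary of success or failure on the endpoints. No model, window or baseline adjustment is named for S/F.

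**The concern.** Improvement in oxygenation is a stated secondary objective (Section 3.2). In the endpoint as written, a series of up to 19 values per patient is reduced to a yes/no result at three times. A cut at 15% loses the size of the change, and each single reading carries the full reading-to-reading noise. The text also does not say whether the 15% must be reached at any one of the three times or at all of them.

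With 10 patients per arm, that choice could decide whether a worthwhile oxygenation effect is visible at all. Section 2.2.3 gives an intravenous half-life generally under 3 minutes, so an effect would be expected while the drug is running. Readings on drug can then be pooled to estimate one average effect with less noise.

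**Working it through.** The plan states no power, SD or correlation, so there is no figure of its own to reproduce.

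**Readings available (current version).** Hour 0 is baseline. The 12-hour reading plus two readings on each of Days 2–10 gives 1 + 2 × 9 = 19 at most. Collection is tied to being on study drug, so early stoppers have fewer. The window from 12 hours to Day 3 gives 1 + 2 × 2 = 5.

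**Assumptions (not in the documents).** SD of log S/F s = 0.30; sustained effect δ = ln 1.20 = 0.182; correlation ρ between readings as shown; n = 10 per arm; two-sided 5%; baseline-adjusted comparison with 20 − 3 = 17 df.

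**Equal correlation.** The residual variance of a mean of k readings given baseline is s²[ρ + (1 − ρ)/k − ρ²]. Power comes from the noncentral t with noncentrality δ/√(2v/10). For ρ = 0.5:
- k = 1: v = 0.09 × 0.75 = 0.0675
- k = 3: v = 0.09 × 0.4167 = 0.0375
- k = 5: v = 0.09 × 0.35 = 0.0315

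| ρ | Power, 1 reading | Power, mean of 3 | Power, mean of 5 | Variance 5 vs 1 | Variance 5 vs 3 |
|---|---|---|---|---|---|
| 0.5 | 32% | 51% | 58% | 0.47 | 0.84 |
| 0.6 | 36% | 56% | 62% | 0.50 | 0.86 |
| 0.7 | 43% | 63% | 69% | 0.53 | 0.87 |

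A mean of all 19 readings has 34% less variance than a mean of three at ρ = 0.5 and 27% less at ρ = 0.7.

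**Unadjusted change from baseline (the measure in 10.3).** In units of s², the variance is (1 − ρ)(1 + 1/k). Three against 19 readings gives (1 + 1/19)/(1 + 1/3) = 0.79, a 21% loss at any ρ; the ceiling with unlimited readings is 1 − 1/(4/3) = 25%.

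**Serially decaying correlation.** Off-diagonal correlation is 0.85 × ρ^|lag|, with ρ from 0.5 to 0.9 per half-day, Day 5 at lag 8 and Day 10 at lag 18, and no missing readings.

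| Summary | Power |
|---|---|
| 12 hours alone | 29–51% |
| Day 5 alone | 25–28% |
| Mean of the three planned readings | 59–64% |
| Mean of five, 12 hours to Day 3 | 49–57% |

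Here the five clustered readings have 5–44% more variance than the three spaced ones.

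**Responder rule (S/F part only, equal correlation).** The SD of the log change is 0.30√(2(1 − ρ)) and the cut is ln 1.15 = 0.140. At ρ = 0.5 the SD is 0.30, so a control patient responds at one time point with probability P(Z > 0.466) = 0.32 and an active patient with P(Z > −0.142) = 0.56. With Fisher's exact test at 10 per arm and ρ from 0.5 to 0.7, power is 7–12% at one time point, 9–15% if any of the three counts, and 5–8% if all three are required.

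**The case against.** A reader might infer that about half the available precision is thrown away, as if the sample had been halved. The documents do not support that. They give no correlation, and the figure of one half holds only against a single reading. Against a mean of the three planned readings the early five-reading mean saves 13–16% under equal correlation, and it can do worse under serial decay. That stands. However, the plan does not provide for averaging its three readings; it scores each one.

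A reader might also infer that the other readings are discarded. They are not. The primary endpoint uses "Change in S/F, oxygenation index and P/F ratio (≥15%) from baseline to 12 hours" and on each of Days 1–10, oxygenation and ventilatory parameters are summarized as safety data (10.8), and patient listings are promised (10.3). None of these is a continuous, baseline-adjusted between-arm estimate. The general rule in 10.3 on mean differences could produce unadjusted mean changes, but it names no oxygenation variable or window.

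Nor does the whole endpoint rest on three times, since the P/F criterion is separate and undated. The power figures cover the S/F part only. The plan names no test for it, and Fisher's test is conservative at this size.

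The trial is declared exploratory, and early, middle and late time points are a legitimate choice. An early mean asks a narrower question. Dose is titrated from 3.4 to 30.6 ng/kg/min (5.3.3), so a short half-life does not guarantee a constant effect. These points limit the claim but do not remove it.

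**Conclusion.** The concern holds in limited form. The S/F part of the secondary endpoint is a responder rule at three times, and no continuous baseline-adjusted comparison is planned, although up to 19 post-baseline values can be computed from data already collected. On the stated assumptions and equal correlation, moving from the responder rule (about 5–15% power) or one continuous reading (32–43%) to an adjusted five-reading mean (58–69%) is a material gain. Most of the gain over the responder rule comes from using a continuous, adjusted summary of several readings. Which readings are averaged matters less, and the direction of that smaller difference depends on the unknown correlation pattern. The improvement is worth making and cheap. The conflict between daily and twice-daily collection is minor but real, since daily recording would leave about 10 post-baseline values instead of 19.

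**What to change.** In 6.2 and 10.6.2, add as the oxygenation comparison each patient's mean log S/F over the twice-daily on-treatment readings in a pre-specified window, compared between arms with adjustment for baseline log S/F and reported with a 95% CI. A window from 12 hours to Day 3 is one option: it limits the loss of readings when treatment ends early for reasons linked to outcome. Use all on-treatment readings to Day 10 as a sensitivity analysis. Keep the 12-hour, Day 5 and Day 10 results as descriptive, and state whether the 15% criterion must be met at any or at all of these times. Reconcile 5.4.2 with Table 2 and Section 9 on how often ventilator parameters are recorded.

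The cost is a few lines of text and no new data. The downside is that an early mean describes the average effect over the first days, not the whole course, and under serial correlation a short window may be less precise than three spaced readings.
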